1.3.5.1 Drug-Related Deaths

Based on reports from the safety data base as of June 30, 2008, there have been reports of death (approximately 1% [28/3000]), deemed by the investigator as possibly related to the administration of study drug. The most common cause of drug related deaths was GI perforation. Other causes included multiorgan failure, sepsis, hypotension, acidosis, and adult respiratory distress syndrome. For details on all drug-related deaths, refer to the current version of the Ipilimumab Investigator Brochure.

1.3.5.2 Safety of 10 mg/kg Multiple Doses

Based on a review of the program-wide SAE data as previously reported, evidence had suggested that ipilimumab-associated IRAEs were dose dependent in frequency, and higher IRAE rates had been observed at 10 mg/kg than at lower doses of ipilimumab. Subsequently, this dose-dependent effect was further demonstrated in CA184-022 in which three dose levels of ipilimumab were studied in subjects with melanoma, including 0.3 vs 3 vs 10 mg/kg. Table 1 summarizes the overall IRAE frequencies by dose from CA184-022 based on safety data from the locked clinical database.

Qualitatively, the safety profile of ipilimumab at 10 mg/kg remains consistent with the low-dose safety profile in that most of the drug-related SAEs are characteristic of immune-related toxicity, and most of the IRAEs are reported in the GI, hepatic, and endocrine systems. However, the data presented in Table 1 suggest that the frequency of IRAEs in association with 10 mg/kg of ipilimumab at multiple doses is higher compared with the IRAE frequency reported for lower doses.

Table 1. Summary of Immune-Related AEs by Treatment Groups - Treated Subjects (CA184-022)

	Number of Subjects (%)			
- -	Ipilimumab			
	0.3 mg/kg (N=72)	3 mg/kg (N=71)	10 mg/kg (N=71)	
Overall irAEs	26.4	64.8	70.4	
Grade 3-4	0	7.0	25.4	
GI irAEs	16.7	32.4	39.4	
Grade 3-4	0	2.8	15.5	
Hepatic irAEs	0	0	2.8	
Grade 3-4	0	0	2.8	
Endocrine irAEs	0	5.6	4.2	
Grade 3-4	0	2.8	1.4	
Skin irAEs	12.5	45.1	46.5	
Grade 3-4	0	1.4	4.2	

1.3.5.3 Neuropathies

Isolated cases of motor neuropathy of an autoimmune origin have been reported among patients treated with ipilimumab. Two cases have been diagnosed as Guillain-Barre syndrome (GBS), only one of which was considered study related. As of July 2, 2008, 15 cases of neuropathy SAEs have been reported. Of these, 13 were assessed as unrelated to study therapy because alternative etiologies, including brain metastases, spinal cord compression, or aterial thrombosis, were identified in almost every case.

1.3.6 Clinical Efficacy of Ipilimumab

Treatment with ipilimumab has demonstrated clinically important and durable tumor responses in several malignancies including melanoma, prostate cancer, and renal cell carcinoma. The most extensively studied tumor type has been malignant melanoma. Based on preliminary results, ipilimumab is active in patients with advanced stage malignant melanoma. The objective responses observed with ipilimumab may be considered durable as they have occurred across a spectrum of doses and schedules.

Based on a preliminary analysis for study MDX010-15 involving ipilimumab 10 mg/kg multiple doses, 34.8% of patients (N = 23) were progression-free at 6 months and about 17.4% were progression-free at 1 year. In comparison, for Study MDX010-08 involving ipilimumab 3 mg/kg multiple doses, 10.8% patients (N = 37) had progression-free survival at 6 months and 8.4% at 1 year. Ipilimumab has also been studied in combination with chemotherapy (dacarbazine), melanoma vaccines (gp100), and cytokines (IL-2). Further details on clinical results can be found in the current version of the Ipilimumab Investigator Brochure.

The clinical benefit of ipilimumab extends to prostate cancer patients as well. A pilot trial looked at the safety and efficacy in 14 prostate cancer patients with bone metastases and varying prior treatment regimens of their prostate cancer.[Small, Clin Cancer Res, 2007]. Half had already received chemotherapy prior to enrollment in the trial. Four patients also had soft tissue disease. Each patient received a single dose of ipilimumab, 3 mg/kg IV. Two patients had a PSA decline of \geq 50%, and each of those patients elected to receive a second dose of ipilimumab 3 mg/kg IV. Neither of those patients had soft tissue lesions that could be measured by RECIST criteria. Their PSA responses lasted for 135 and 60 days, respectively.

More recently, 45 patients with metastatic, castration-resistant prostate cancer were given ipilimumab 10 mg/kg every three weeks for four doses. Twenty-nine of the patients received a single dose of radiation just prior to the first dose of ipilimumab. Of these 29 patients, 14 had no exposure to chemotherapy prior to ipilimumab treatment, and 15 had received chemotherapy prior to ipilimumab treatment. The use of chemotherapy was historical, and not part of this study. The patients with a PSA decline of \geq 50% were more likely to be chemotherapy naïve. The results are in Table 2. Importantly, response to ipilimumab appears to be increased with this dose and schedule, over the 3 mg/kg x1.

Table 2. Summary of PSA decline in men with advanced prostate cancer who were treated with ipilimumab with and without radiation and who either had or had not been previously treated with chemotherapy.

Sub group	Ipi alone	XRT + Ipi No chemo	XRT + Ipi Chemo	All Ipi alone	All XRT + Ipi	All No Chemo	All Chemo
N (45 patients total	16	15	14	16	29	27	18
≥ 50% PSA↓	5	4	1	5	5	8	2

This study did not formally compare ipilimumab with radiation versus ipilimumab alone. The data presented in Table 2 does not overwhelmingly support or refute the usefulness of radiation added to ipilimumab.

1.3.6.1 Relationship Between Response and Immune Breakthrough Events in Patients with Metastatic Melanoma and Prostate Cancer

Drug-related AEs of any grade considered to be immune-mediated in nature (IRAEs) were reported for 54.0% of subjects in clinical studies of ipilimumab. These IRAEs are a consequence of inhibiting CTLA-4 function and most were reported as Grade 1 or 2. An association between BORR and higher grade (Grade 3-4) IRAEs was suggested in early studies of ipilimumab 3 mg/kg but this association was not observed in 4 Phase 2 studies of ipilimumab (CA184022, CA184008, CA184007 and CA184004). There were proportionally more subjects with IRAEs of any grade who experienced response or stable disease, but due to the small sample sizes, these observations were statistically inconclusive. 21,22,23

1.4 Overall Risk/Benefit Assessment melanoma and prostate cancer

Results from the 3 primary efficacy studies of ipilimumab suggest that the 10 mg/kg dose is active and offers the best benefit to risk ratio based on a 27.1% to 35.1% rate of disease control and a favorable 1-year survival rate of 48.6% to 59.1% compared with that reported in the literature (25.5% to 35%). ^{24,25,26,27} Substantial reductions in total tumor burden, including widely disseminated disease in the skin, lung, and/or other visceral

disease sites, were reported. More than half the responses were reported in subjects staged with M1b or M1c advanced melanoma disease, which is most resistant to approved therapies. The kinetics of ipilimumab resulted in known patterns of clinical activity (CR, PR and SD) as well as novel patterns, characterized by reductions in total tumor burden, including existing and new lesions, after initial tumor volume increase and/or after appearance of new lesions. In the pretreated population at 10 mg/kg in 2 of the 3 studies, disease control after initial tumor volume increase and/or new lesions was reported for 9.7% of subjects. Across all 3 studies, stable disease was often accompanied by clinically relevant reductions in tumor burden compared to baseline. All patterns of response, including SD, appeared to result in favorable survival, based on 1-year survival rates.

Characteristic organ-specific inflammatory IRAEs were reported with ipilimumab therapy, typically during induction therapy. IRAEs were mostly reversible within days to weeks following cessation of therapy or treatment with symptomatic therapy, corticosteroids or other anti-inflammatory agents, depending upon severity. Accumulated clinical experience resulted in detailed toxicity management guidelines (also termed algorithms), by use of which IRAEs can be effectively managed, especially when IRAEs are recognized early and subjects are treated in a timely fashion. This can minimize the occurrence of IRAE complications, such as GI perforation/colectomy or hepatic failure.

Treatment with ipilimumab resulted in clinical activity in pretreated and previously untreated subjects with advanced melanoma. Clinically relevant reductions in the tumor burden from baseline were reported, together with a preliminary evidence of improved overall survival compared with published survival rates. These findings, together with evidence of a safety profile that is manageable with careful monitoring and appropriate intervention for treatment of immune-related toxicities, suggest an acceptable benefit to risk ratio.

Men with metastatic prostate cancer who do not obtain and maintain a complete biochemical response (PSA \leq 0.2 ng/ml) to AST alone have a very poor prognosis.² The median survival of this study population is only 13 to 44 months, where a PSA > 4.0 ng/ml after induction AST has the shortest median survival. Chemotherapy using docetaxel with prednisone is currently an option for men with CRPC. While there have been no direct comparisons of toxicity between ipilimumab and docetaxel, we anticipate that the overall toxicity of chemotherapy is greater. Since the initial approval of this study, several other agents have gained approval in CRPC, namely abiraterone with

prednisone, enzalutamide and sipuleucel-T. Although they have been shown to improve overall survival, their benefit compared to placebo is on the order of 2-4 months, and there is still a clear need to improve survival in this group. Furthermore treatment with ipilimumab does not disqualify patients from being treated with these other agents.

The early identification of this aggressive subset of metastatic prostate cancer offers significant opportunities for benefit in the form of delayed progression and longer survival with successful intervention. The overall risk-benefit ratio for patients entering this protocol is therefore at least comparable to and possibly better than alternative options.

1.5 Study Rationale

Ipilimumab is a natural choice for early intervention for several reasons. While there can be significant toxicities during the acute phase of treatment, the toxicities are almost always manageable and resolve with time-limited treatment. Thus, long-term toxicities in men who benefit from this intervention are unlikely. Immunotherapy may be more effective when disease burden is limited. Treating this population early will ensure that they have a relatively low volume of disease. This therapy has been shown to be active in patients who have extremely aggressive disease. We are targeting the same patients but at an earlier time point in the course of their disease. The overall risk benefit ratio for patients entering this protocol is therefore at least comparable to, and possibly better than alternative options.

This is a single arm phase II study to examine the activity and safety of ipilimumab early in the course of metastatic prostate cancer, in patients with an incomplete response to androgen suppression therapy. Men who do not achieve a complete response to AST have a significantly shortened median survival. Early immune-based therapy may delay disease progression and prolong survival in this subset of patients.

The primary endpoint is the fraction of patients who achieve an undetectable PSA (≤ 0.2 ng/ml). The Hussain paper has shown that men who achieve and maintain an undetectable PSA have a significantly longer median survival.² We will recruit 30 men to this study.

Secondary endpoints include time to PSA progression, time to progression by any measure, time to death from any cause, number of patients with immune breakthrough events and correlation of these with PSA declines and correlative studies looking at the

ratios of T regulatory cells and T effector cells before each of the first four doses of ipilimumab.

2 STUDY OBJECTIVES

2.1 Primary Objective

Proportion of patients who achieve an undetectable PSA (≤ 0.2 ng/ml) after initiation of Ipilimumab therapy.

2.2 Secondary Objectives

- Time to PSA progression
- Time to progression by any measure
- Maximum percentage of PSA reduction in each patient
- Number of patients with IRAEs and correlation of these with complete PSA response, time to progression, and T cell measurements
- Measures of T cell response to therapy with flow cytometry
- Response in Measurable disease by modified RECIST criteria
- Time to death from any cause.
- To examine correlative biomarkers and their relationship to clinical outcomes. Potential biomarkers include, but are not limited to CRP, IGF-1 and -2, or FSH.
- Bank samples for future molecular correlative studies, biomarker, or other studies.

3 STUDY DESIGN

3.1 Pre-treatment Evaluation

- 3.1.1 Clinical evaluation
 - Patient's eligibility will be determined with the aid of an eligibility checklist.
 - Eligible patients will be informed of the details of the study, including potential risks and benefits.
 - Signed, informed consent will be obtained before any study-related procedures occur.

- o A complete patient history and physical examination will be done.
- All concomitant medications including vitamins, herbs, and supplements will be recorded.

3.1.2 Laboratory

All screening labs must be done within 28 days of first treatment. Cycle 1 Day 1 labs do not need to be repeated if screening labs were within 7 days of Cycle 1 Day 1.

- Serum PSA.
- Complete Blood Count with automated differential
- Chemistry panel including ALT, AST, Alkaline Phosphatase, Total or Direct Bilirubin, BUN, Creatinine, Electrolytes (Sodium, Potassium and Chloride), Calcium, and Glucose
- Autoimmune panel including TSH and free T4
- o LDH
- Testosterone
- Investigational blood samples will be obtained within 0 to 7 days prior to treatment (for the baseline) and just prior to each of doses of Cycle 2, 3,
 4.
- O Hepatitis panel and HIV will be tested if the study patient has engaged in high risk behaviors, such as using intravenous drugs or engaging in unprotected sex outside of a long term relationship. This determination will be made by the treating oncologist.

3.1.3 Imaging and Diagnostic

A radionuclide bone scan and CT scan (chest, abdomen and pelvis) will be obtained at baseline within 28 days of initiation of treatment.

3.2 Registration Procedure

A centralized registration procedure will be used. After eligibility screening, patients selected to participate will be registered with the lead center (OHSU) first, then their study site/institution.

3.2.1 **Lead Site Registration**: To initiate lead site registration, study sites/institutions should forward copies of the signed informed consent, HIPAA research authorization, the study registration form (eligibility checklist), plus all source documentation verifying eligibility, to the lead center by fax or e-mail. Upon receipt of these forms, sponsor will confirm patient eligibility with study personnel; assign a unique patient study identification number, and complete

patient registration. Treatment must not commence until the patient has received his identification number.

Patient Registration: [name], OHSU [contact] [contact]

Email: [contact]

- 3.2.2 Institutional Registration: Patient registration at each study site/institution will be conducted according to the institution's established policies. Prior to registration, patients will be asked to sign and date an Institutional Review Board (IRB)-approved consent form and HIPAA research authorization. 3.3 Follow up with Monitoring, Dose Delays and Dose Modifications
 - 3.3.1 During the first four doses of ipilimumab treatment:
 - o Adverse events will be recorded every 3 weeks or as they occur.
 - Physical examination and vital signs will be performed every 3 weeks and documented in the medical record.
 - Complete Blood Count with automated differential, PSA, Chemistry Panel (Calcium, ALT, AST, Alkaline Phosphatase, Total Bilirubin, BUN, Creatinine, Glucose, Sodium, Potassium, Chloride) and Autoimmune Panel (,TSH, free T4) will be obtained on day 1 of the first four 21-day cycles.
 - Available lab results will be reviewed prior to administration of ipilimumab.
 - o Imaging: A radionuclide bone scan and CT scan (chest, abdomen and pelvis) will be obtained at baseline, week 12, week 24, and every three months thereafter until radiographic progression. Scans may be obtained sooner for concerning symptoms.
 - Correlation studies: Investigational serum samples will be obtained at baseline and on the first day of cycles 2 through 4. See Appendix 7 for details. Baseline draw will occur within 7 days of the first dose and must occur before the treatment dose is administered.
 - 3.3.2 After Completion of initial 4 cycles of ipilimumab:
 - Serum PSA will be drawn every 6 weeks for weeks 12-24, then every 12 weeks.
 - Complete blood count with automatic differential, comprehensive chemistry panel and Autoimmune Panel (TSH, free T4) will be obtained prior to administration of each dose of ipilimumab, which will be given to eligible patients every 12 weeks beginning at week 24.

- Available lab results (i.e. chemistries and blood counts) will be reviewed prior to administration of ipilimumab.
- o Imaging and Diagnostic: A radionuclide bone scan and CT scan (chest, abdomen and pelvis) will be obtained at baseline, week 12, week 24, and every three months thereafter until radiographic progression. Scans may be obtained sooner for concerning symptoms.

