Patients with a life expectancy less than 6 months, treatment with any investigational agent in the last 28 days, more than 18 months since initiation of AST, or a concurrent active malignancy diagnosed within the last 5 years (other than non-melanoma skin cancer, or other readily treatable tumors with expected cure) will not be eligible for this study. Patients must not have a known autoimmune disease, use prednisone > 10 mg daily (or its equivalent) orally for any indication, or have chronic infections (including hepatitis B or C or HIV).

Criteria for Evaluation: (Efficacy, safety, stopping rules, etc.)

Patients will receive a history and physical exam and multiple laboratory tests (PSA, complete chemistry panel and blood counts, as well as tests for endocrinopathies) at baseline and every 3 weeks during the first 4 doses of therapy. Available labs (i.e. the chemistry panel and blood counts) will be reviewed prior to administration of ipilimumab. Imaging studies will be done at baseline, 12 weeks, 24 weeks and then every six months, or sooner if concerning symptoms arise. If there is no evidence of radiographic progression on the 24-week scan, patients will go on to receive four doses of maintenance ipilimumab therapy (weeks 24, 36, 48, 60). They will have a history and physical exam at least every three months. Their survival status will be assessed by phone survey every 6 months for up to five years after the last study visit.

Efficacy will be based on the results of the PSA and imaging studies (using PCWG2 and modified RECIST criteria). Safety will be monitored using the regular physician examinations and laboratory assessments.

Statistics:

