6 STUDY PROCEDURES AND OBSERVATIONS

6.1 Time and Events Schedule for Protocol CA184059

		Induction* (Cycles 1-4)			Between Treatments			Maintenance* (Cycles 5-8)			Every 6 Month Follow Up*		
T //P 1	Scree . #	Wk	Wk	Wk	Wk	Wk	Wk	Wk	11/1 24	WI 26	XX/1 40	W/I (0	Evel Fc
Test / Procedure	ning#	1	4	/	10	12	18	23/24	Wk 24	Wk 36	Wk 48	Wk 60	Π
Informed Consent	X												
Inclusion / Exclusion Criteria	X												
Demographics, medical history, concurrent medical conditions	X												
Testosterone level	X												
Serum samples for hepatitis panel and HIV, if high index of suspicion	X												
ECOG performance status	X	X	X	X	X	X	X	X	X	X	X	X	
Blood collection for correlative studies ¹		X	X	X	X								
Physical Exam	X	X	X	X	X	X	X	X	X	X	X	X	
Vital Signs	X	X	X	X	X	X	X	X	X	X	X	X	
Weight		X	X	X	X				X	X	X	X	
Bone Scan ²	X					X		X		X	X	X	
Chest, Abdomen & Pelvis CT ²	X					X		X		X	X	X	

CBC with differential	X	X	X	X	X	X	X	X	X	X	X	X	
Chemistry Panel: Creatinine, BUN, electrolytes (sodium, potassium, chloride), glucose, bilirubin alkaline phosphatase, ALT, AST, calcium, ³	X	X	X	X	X	X	X	Х	Х	X	Х	X	
LDH	X												
Autoimmune Profile: TSH, free T4	X	X	X	X	X				X	X	X	X	
PSA ⁴	X	X	X	X	X	X	X	X	X	X	X	X	
Concurrent medications (include documentation of androgen suppression therapy)	X	X	X	X	X				X	X	X	X	
Adverse Effects Recorded	X	X	X	X	X		_		X	X	X	X	
Ipilimumab		X	X	X	X				X	X	X	X	
Telephone Contact													X

^{*} Cycle 1-8 procedures can be done +/- 3 days and Long Term Follow-Up can be done +/- 2 weeks.

#Screening procedures must be done within 28 days of first treatment

^{**}PSA, Autoimmune profile, LDH, CBC Diff, Chem panel including Creatinine, BUN, electrolytes (sodium, potassium, chloride), glucose, bilirubin, alkaline phosphatase, ALT, AST, calcium, phosphorus and Correlative **baseline samples** DO NOT need to be repeated on Cycle 1 Day 1 if done within 7 Days of Cycle 1 Day 1

¹ Per outlined correlative studies

² Imaging Studies will also be done every three months until radiographic progression

³ Available labs (i.e. chemistries and blood counts) will be reviewed prior to each infusion

⁴ PSA will be done until radiographic progression

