6.2 Procedures by Visit

The Time and Events Schedule summarizes the frequency and timing of various measurements.

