7.3.1 Serious Adverse Events

Following the subject's written consent to participate in the study, all SAEs must be collected, including those thought to be associated with protocol-specified procedures. All SAEs must be collected that occur within 70 days of discontinuation of dosing of the investigational product. If applicable, SAEs must be collected that relate to any later protocol-specified procedure (eg, a follow-up skin biopsy). The investigator should notify

BMS of any SAE occurring after this time period that is believed to be certainly,

probably, or possibly related to the investigational product or protocol-specified

procedure.

All SAEs whether related or unrelated to the ipilimumab, must be immediately reported

to BMS (by the investigator or designee) within 24 hours of becoming aware of the event.

If only limited information is initially available, follow-up reports are required. The

original SAE form must be kept on file at the study site.

Participating centers will notify the Lead Site, OHSU, of all SAEs within 24 hours of

becoming aware of the event. Reporting will occur by MedWatch Form 3500A with

supporting documentation. OHSU will report this information to BMS and/or the FDA,

as appropriate.

All SAEs should be faxed or emailed to BMS at:

Global Pharmacovigilance & Epidemiology

Bristol-Myers Squibb Company

[contact]

Email: [contact]

For studies conducted under an Investigator IND, any event that is both serious and

unexpected must be reported to the FDA as soon as possible and, in no event, later than 7

days (death or life-threatening event) or 15 days (all other SAEs) after the investigator's

or institution's initial receipt of the information. BMS will be provided with a

simultaneous copy of all adverse events filed with the FDA. SAEs should be reported on

the MedWatch Form 3500A, which can be accessed at:

http://www.accessdata.fda.gov/scripts/medwatch/.

MedWatch SAE forms should be sent to the FDA at:

MEDWATCH

[name]

[name]

Fax: [name] ([name])

http://www.accessdata.fda.gov/scripts/medwatch/

All SAEs should simultaneously be faxed or e-mailed to BMS at:

Ipilimumab IST Protocol Shell, Version 7: 17 March 2009

54

Global Pharmacovigilance & Epidemiology Bristol-Myers Squibb Company

[contact]

Email: [contact]

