8.5 Statistical Analysis Plan

Demographic and clinical characteristics will be summarized using descriptive statistics (e.g. proportions, mean, standard deviation, median, range). The proportion of patients who achieve an undetectable PSA (≤ 0.2 ng/ml) after initiation of ipilimumab therapy will be provided with the exact 95% confidence interval. The Kaplan-Meier method will be used to estimate time to PSA progression, time to disease progression by any measure and time to death from any cause. In evaluation of time to PSA progression and time to disease progression by any measure will be censored for:

- 1) lost to follow-up at the date of last contact
- 2) use of additional cancer therapies that would interfere with ascertainment of the endpoint of interest
- death from a causes other than prostate cancer or treatment of prostate cancer.

Evaluation of time to death will be censored for lost to follow-up at last contact.

The effects of IRAEs and other immune parameters (e.g., a ratio of T regulatory cells to T effector cells) on clinical outcomes will be evaluated using logistic regression for binary endpoints (e.g., achievement of undetectable PSA) and Cox regression for the time to event outcomes (e.g., time to PSA progression).

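### Section 8.5 relates immune-related events to time-to-event outcomes without saying when event status is fixed; separately, no thyroid test is scheduled between weeks 10 and 24

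*Combined protocol and SAP*

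**What the plan says.** **Analysis.** A secondary objective in section 2.2 reads: "Number of patients with IRAEs and correlation of these with complete PSA response, time to progression, and T cell measurements". Section 8.5, like the synopsis statistics, assesses the effects of IRAEs and other immune parameters by logistic regression for binary outcomes and by "Cox regression for the time to event outcomes (e.g., time to PSA progression"). Neither place gives a landmark, a time-dependent covariate or a cut-off date for IRAE status. Section 7.3 does require the onset of every adverse event to be captured.

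**Who continues.** The synopsis states: "If there is no evidence of radiographic progression on the 24-week scan, patients will go on to receive four doses of maintenance ipilimumab therapy". Sections 3.5 and 5 agree. After radiographic progression, section 3.6 moves men to semi-annual phone surveys of treatment status and survival.

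**Thyroid testing.** Section 3.3.1 schedules TSH/free T4 on day 1 of the first four cycles. Section 3.3.2 then ties the panel to dosing: "Autoimmune Panel (TSH, free T4) will be obtained prior to administration of each dose of ipilimumab, which will be given to eligible patients". The first such dose is due at week 24. In section 6.1 the row "Autoimmune Profile: TSH, free T4" is marked at screening and weeks 1, 4, 7 and 10, blank at weeks 12, 18 and 23/24, and marked again in the maintenance columns. Blood counts, chemistry and PSA are marked at all three blank weeks. The adverse effects row shows no mark at those weeks either. Appendix 3 asks for TSH/free T4 when unexplained symptoms suggest an endocrine problem.

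**The concern.** IRAE status is not known at the start of treatment. A man can be counted as having a late IRAE only if he has been followed, and in part dosed and tested, for long enough to show one. After week 24 that opportunity depends on not having progressed. If status is treated as fixed from the start, the weeks before onset, when he was by definition still event-free, are credited to the IRAE group. The association then leans towards benefit even if IRAEs have no bearing on outcome. Whether immune toxicity goes with tumour control is one of the questions this study sets out to explore, so the direction of that error matters.

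The thyroid gap is a related but separable matter. A thyroid event without clear symptoms is found only by a test, and the last scheduled test for a man who does not reach maintenance is drawn before his fourth dose.

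**Working it through.** The plan gives no figure of its own on this point, so the check is of the schedule and of what the model would do with it.

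**1. The gap in scheduled tests (sections 3.3.1, 3.3.2, 6.1).**
- Week 24 − week 10 = 14 weeks = 98 days. With the 6.1 window of ±3 days at each end: 92 to 104 days.
- With a week 18 test: 18 − 10 = 8 weeks and 24 − 18 = 6 weeks.

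**2. What depends on progression.**

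| | No maintenance | Full maintenance |
|---|---|---|
| Doses after dose 4 | 0 | 4 (weeks 24, 36, 48, 60) |
| Scheduled TSH/free T4 after dose 4 | 0 | 4 |
| Scheduled TSH/free T4 from week 1 on | 4 | 4 + 4 = 8 |

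Through week 12 there is no such split. Section 3.5 defers the assessment of progression until the four cycles are complete, and section 5.1.4 stops therapy for radiographic progression only after 12 weeks. Men still in follow-up have the same scheduled doses and tests up to then.

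**3. How the Cox model is affected.** Take a man with IRAE onset at week 36 and progression at week 48. With status fixed from the start, all 48 weeks count as IRAE-positive. With status switched on at onset, 36 weeks count as IRAE-negative and 48 − 36 = 12 weeks as positive. The first coding hands 36 guaranteed progression-free weeks to the IRAE group.

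**4. An illustration of direction, not of size.** Assumptions not in the documents: 30 men; no true IRAE effect; exponential progression with median 24, 40 or 60 weeks; onset uniform over weeks 2 to 24; follow-up cut at week 104. IRAE frequency is 60% (section 1.3.5) or 70.4% (Table 1). There were 600 simulated trials per setting.

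| IRAE coding | Median hazard ratio | Rejections at nominal 5% |
|---|---|---|
| Any IRAE before progression, fixed from start | 0.47–0.64 | 16–49% |
| Time-dependent | 0.97–1.03 | 4–8% |
| Week 12 landmark | 0.99–1.05 | 4–6% |

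Some fits did not converge, and one median was not computable for each of the first and third codings. Maintenance dosing and detection are not modelled, so this shows only the effect of crediting time before onset.

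**5. Why one coding does not serve every outcome.** For the progression endpoints a time-dependent covariate works, because the men at risk are those still being followed for that endpoint. For death it does not. Scheduled testing ends at radiographic progression while survival follow-up continues (section 3.6), so new IRAEs would be found less often in men already at higher risk. A landmark set before maintenance eligibility separates the men avoids this.

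**6. Scale of the thyroid point.** Table 1 gives endocrine events of 4.2% among 71 melanoma subjects at 10 mg/kg: 0.042 × 71 ≈ 3. The exact 95% interval for 3/71 is 0.9% to 11.9%. Scaled to 30 men this is 30 × 3/71 ≈ 1.3 (0.3 to 3.6). The table does not separate thyroid from other endocrine events.

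**The case against.** Section 8.5 does not prescribe an ever/never indicator; it is silent, and the onset dates needed for a better coding are already collected. Section 1.4 puts IRAEs typically in induction, and radiographic progression is not assessed until induction ends, so early IRAEs create little guaranteed event-free time for that endpoint. This stands and reduces the likely bias. It does not remove it: later IRAEs remain. PSA progression, the example in 8.5, can also be reached during induction, since PSA is drawn every 3 weeks and needs confirmation only 3 weeks later (section 6.4.2.1).

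The thyroid schedule can be defended as a consistent pre-dose panel. Physical examinations at weeks 12, 18 and 23/24 and symptom-driven testing remain. That is fair, and it is why the safety point is small. Consistency still leaves a progressing man without a scheduled test after dose 4.

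It is also true that a week 18 draw is itself outcome-dependent. A week 12 progression confirmed at least 4 weeks later can take a man off visits from 12 + 4 = week 16. The week 18 and week 24 tests must therefore stay out of any fixed window used for the association.

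Several stronger inferences are tempting and do not hold:
- Section 7.3.1 says "All SAEs must be collected that occur within 70 days of discontinuation of dosing of the investigational product", and week 18 falls inside that period. That is no argument for testing then, because a thyroid event without symptoms would not ordinarily be serious under section 7.1.1.
- A reader might infer that no progression can be confirmed before week 16. The repeat-scan rule in section 5.1.4 covers radiographic progression only.
- Section 3.3.2 might seem to leave blood counts and chemistry uncovered between weeks 12 and 24. It does not: section 6.2 says "The Time and Events Schedule summarizes the frequency and timing of various measurements", and 6.1 marks both at weeks 12, 18 and 23/24.

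**Conclusion.** The point holds, as a minor one, and its main part is the analysis. If IRAE status is counted over all follow-up and treated as fixed from the start, the Cox estimates will lean towards benefit for IRAEs of every kind, thyroid or not. This rests on two things: that coding, which 8.5 permits but does not state, and the dependence of dosing and testing from week 24 on radiographic progression, which the plan does state. The amount of bias cannot be derived from the documents, and the simulated hazard ratios should not be read as an estimate of it.

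The safety part is a 14-week interval without a scheduled thyroid test, and no scheduled test after dose 4 for men who progress by week 24. A reader might infer a serious monitoring failure; the remaining examinations, the symptom-driven work-up and an expected endocrine count of about 1.3 in 30 men do not support that. Nor is the primary endpoint or its 6-of-30 rule touched, since neither uses IRAE status.

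**What to change.** **In section 8.5 and the synopsis statistics:**
- Time to PSA progression and time to any progression: enter IRAE as a time-dependent covariate that switches on at the recorded onset date.
- Time to death: use a landmark, for example week 12, with IRAE status as known then.
- Any landmark: include only men free, at that time, of the specific endpoint being analysed.
- Logistic model for undetectable PSA: count IRAEs through week 12, which leaves out the week 18 and week 24 tests. Read the result as an association, since an early PSA response may precede the IRAE.
- List later IRAEs descriptively.

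**In sections 3.3.2 and 6.1:** add TSH/free T4 to the existing week 18 draw, and mark adverse event recording at that visit, for all men still attending whether or not they will receive maintenance.

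**Cost.** The analysis change is wording and uses dates already collected. The landmark and the fixed window give up later IRAEs, and with at most 30 men every estimate will be imprecise. The laboratory change is 30 × 1 = 30 assays at most (10 if the trial stops after stage 1) and no extra visit. It will miss men who have already moved to phone follow-up.
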